5.6.4 Vital Signs

Descriptive statistics for vital signs parameters (systolic and diastolic BP, pulse, temperature, and weight) and changes from baseline will be presented by visit and treatment group.

Subject data listings will be provided.

5.6.5 Electrocardiograms

Shift tables will be presented changes from baseline in 12-lead ECG interpretation (normal/abnormal, not clinically significant/abnormal, not clinically significant) by visit and treatment group.

Subject data listings will be provided.

5.6.6 Other Safety Analyses

5.6.6.1 Chest X-Ray

Shift tables will be presented changes from baseline in chest x-ray (normal/abnormal, not clinically significant/abnormal, not clinically significant) by visit and treatment group.

Subject data listings will be provided.

5.6.6.2 Neurological findings

Descriptive statistics for neurological findings will be presented by visit and treatment group.

Subject data listings will be provided.

5.6.6.3 Blood CD4 positive cell counts

For Blood CD4 positive cell counts, the actual value and the change from baseline to each postbaseline visit will be summarized by visit and treatment group using descriptive statistics. Blood CD4 positive cell counts will be assigned a low/normal/high (LNH) classification according to whether the value was below (L), within (N), or above (H) the it's reference range. Within-treatment comparisons will be based shift tables that compare the baseline LNH classification to the LNH classification at each postbaseline visit.

Subject data listings will be provided.

5.7 Other Analyses

5.7.1 Anti-JCV Antibody Test

Anti-JCV antibody test result (positive or negative) is judged according to the results of screen assay and inhibition assay.

Subject data listings will be provided.

5.8 Exploratory Analyses

Exploratory analyses may be conducted as appropriate. Any exploratory analyses that are performed will be appropriate titled and labeled as exploratory and will be clearly distinguished from planned analyses when results are reported in the Clinical Study Report.

6 INTERIM ANALYSES

No interim analyses are planned for this study.

7 CHANGES IN THE PLANNED ANALYSES

Changes in the planned analyses for protocol are as follows:

- Based on the protocol amendment Version 6, all efficacy results will be summarized until week 84.
- Regarding the PK analysis for extension phase, only listing will be created.

8 DEFINITIONS AND CONVENTIONS FOR DATA HANDLING

8.1 Baseline, Time Windows for statistical analyses

8.1.1 Definition of baseline value

The baseline value was defined as the most recent value reported just before first dosing.

8.1.2 Definition of change from baseline and percent change from baseline

Change from baseline is defined as postbaseline value minus baseline value. Percent change from baseline is defined as follows:

$$\% \text{ Change from baseline} = (\text{Change from baseline}/\text{Baseline}) * 100$$

For any Baseline value of 0, the subject's corresponding percent change from baseline will not be included in the summary statistics table.

Table 8.4 Definition of time windows and calculated visits for 12-lead ECG, Chest x-ray, Pregnancy test, Blood CD4 positive cells

Visit	Base date	Time windows
Week 12 - Week 24 by 12 weeks	Date-time of first drug administration + X * 7 days (Week X)	Base date - 14 days <= < Base date + 14 days
Week 52	Date of first drug administration + 334 days	Base date - 14 days <= < Base date + 14 days
Week 76	Date-time of first drug administration + 532 days	Base date - 14 days <= < Base date + 14 days
Week 104	Date-time of first drug administration + 728 days	Base date - 14 days <= < Base date + 14 days

Table 8.5 Definition of time windows and calculated visits for body weight, Autoantibody

Visit	Base date	Time windows
Week 12 - Week 36 by 12 weeks	Date-time of first drug administration + X * 7 days (Week X)	Base date - 14 days <= < Base date + 14 days
Week 52	Date of first drug administration + 334 days	Base date - 14 days <= < Base date + 14 days
Week 104	Date-time of first drug administration + 728 days	Base date - 14 days <= < Base date + 14 days

Table 8.6 Definition of time windows and calculated visits for Neurological findings, Vasculitis marker tests

Visit	Base date	Time windows
Week 12 - Week 36 by 12 weeks	Date-time of first drug administration + X * 7 days (Week X)	Base date - 14 days <= < Base date + 14 days

Week 52 - Week 88 by 12 weeks	Date-time of first drug administration + X * 7 days (Week X)	Base date - 14 days <= < Base date + 14 days
Week 104	Date-time of first drug administration + 728 days	Base date - 14 days <= < Base date + 14 days

Table 8.7 Definition of time windows and calculated visits for Serum KL-6, β D glucan, Serum TRACP-5b concentration, VectraTM DA

Visit	Base date	Time windows
Week 12 - Week 24 by 12 weeks	Date-time of first drug administration + X * 7 days (Week X)	Base date - 14 days <= < Base date + 14 days
Week 52	Date of first drug administration + 334 days	Base date - 14 days <= < Base date + 14 days
Week 104	Date-time of first drug administration + 728 days	Base date - 14 days <= < Base date + 14 days

Table 8.8 Definition of time windows and calculated visits for Serum anti-E6011 antibody

Visit	Base date	Time windows
Week 4 (Day 29)	Date-time of first drug administration + 28 days	Base date - 7 days <= < Base date + 14 days
Week 8 - Week 104 by 4 weeks	Date-time of first drug administration + X * 7 days (Week X)	Base date - 14 days <= < Base date + 14 days

Table 8.9 Definition of time windows and calculated visits for Serum cytokine concentration, LRG1, Ang2

Visit	Base date	Time windows
Week 4 (Day 29)	Date-time of first drug administration + 28 days	Base date - 7 days <= < Base date + 14 days
Week 12 - Week 24 by 12 weeks	Date-time of first drug administration + X * 7 days (Week X)	Base date - 14 days <= < Base date + 14 days
Week 52	Date of first drug administration + 334 days	Base date - 14 days <= < Base date + 14 days
Week 104	Date-time of first drug administration + 728 days	Base date - 14 days <= < Base date + 14 days

Table 8.10 Definition of time windows and calculated visits for Anti-JCV antibody test

Visit	Base date	Time windows
Week 24	Date-time of first drug administration + 168 days	Base date - 14 days <= < Base date + 14 days
Week 52	Date of first drug administration + 334 days	Base date - 14 days <= < Base date + 14 days
Week 76	Date-time of first drug administration + 532 days	Base date - 14 days <= < Base date + 14 days
Week 104	Date-time of first drug administration + 728 days	Base date - 14 days <= < Base date + 14 days

Table 8.11 Definition of time windows and calculated visits for Virus test, Syphilis test, Tuberculosis test

Visit	Base date	Time windows
Week 52	Date of first drug administration + 334 days	Base date - 14 days <= < Base date + 14 days
Week 104	Date-time of first drug administration + 728 days	Base date - 14 days <= < Base date + 14 days

Table 8.12 Definition of time windows and calculated visits for Joint x-ray

Visit	Base date	Time windows
Week 0	Date-time of first drug administration	Base date <= 28 days
Week 24	Date-time of first drug administration + 168 days	28 days <= Base date + 28 days
Week 52	Date of first drug administration + 334 days	Base date - 28 days <= < Base date + 28 days
Week 76	Date-time of first drug administration + 532 days	Base date - 28 days <= < Base date + 28 days

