9.5.1.5.6 ELECTROCARDIOGRAMS

Electrocardiograms will be obtained at the visits specified in the Schedule of Procedures/Assessments ([Section 9.5.2.1, Table 4](#)). Standard 12-lead ECG recordings will be used. Subjects must be in the supine position for 5 minutes prior to ECG. The investigator or subinvestigator records the results (abnormal or normal) in the CRF. If blood sampling is planned at the same timeframe and ECG is performed after blood collection, ECG must be carried out after sufficient time to avoid potential influence of blood collection on ECG.

An ECG abnormality may meet the criteria of an AE as described in this protocol ([Section 9.5.1.5.1](#)) and the CRF Completion Guidelines. In these instances, the ECG abnormality will be recorded as an AE in the CRF.

For ECG abnormalities meeting the criteria of an SAE ([Section 9.5.1.5.2](#)), the investigator must report the sponsor using the SAE form (with the ECG report) via fax, or other means of transmission (see “Reporting of Serious Adverse Events”).

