9.5.5 Completion/Discontinuation of Subjects

A subject may elect to discontinue the study at any time for any reason. All subjects who discontinue the study are to complete the study's early discontinuation procedures indicated in the Schedule of Procedures/Assessments ([Section 9.5.2.1, Table 4](#)).

The investigator will promptly explain to the subject involved that the study will be discontinued for that subject and provide appropriate medical treatment and other necessary measures for the subject. A subject who has ceased to return for visits will be followed up by mail, phone, or other means to gather information such as the reason for failure to return, the

status of treatment compliance, the presence or absence of AEs, and clinical courses of signs and symptoms.

Subjects who discontinue early from the study will be discontinued for 1 of these primary reasons: AE(s), lost to follow-up, subject choice, inadequate therapeutic effect, progression of disease, withdrawal of consent, pregnancy, study terminated by sponsor, or other. In addition to the primary reason, the subject may indicate 1 or more secondary reason(s) for discontinuation. Study disposition information will be collected on the CRF.

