5.6.3 Laboratory Values

Laboratory results will be summarized using Système International (SI) units. For quantitative parameters listed in [protocol Section 9.5.1.5.3](#), the actual value and the change from baseline to each postbaseline visit will be summarized by visit and treatment group using descriptive statistics. Qualitative parameters listed in protocol Section 9.5.1.5.3 will be summarized using frequencies (number and percentage of subjects), and changes from baseline to each postbaseline visit and to end of treatment will be reported using shift tables. Percentages will be based on the number of subjects with both nonmissing baseline and relevant postbaseline results.

Laboratory test results will be assigned a low/normal/high (LNH) classification according to whether the value was below (L), within (N), or above (H) the laboratory parameter's reference

range. Within-treatment comparisons for each laboratory parameter will be based on 3-by-3 tables (shift tables) that compare the baseline LNH classification to the LNH classification at each postbaseline visit and at the end of treatment. Similar shift tables will be used to compare the baseline LNH classification to the LNH classification for the highest and lowest value during the study.

The Sponsor's Grading for Laboratory Values using CTCAE v4.0 presents the criteria that will be used to identify subjects with treatment-emergent markedly abnormal laboratory values (TEMAVs). Except for phosphate, a TEMA is defined as a postbaseline value with an increase from baseline to a grade of 2 or higher. For phosphate, a TEMA is defined as a postbaseline value with an increase from baseline to a grade of 3 or higher. When displaying the incidence of TEMAVs, each subject will be counted once in the laboratory parameter high and in the laboratory parameter low categories, as applicable.

Laboratory results versus visit by treatment group will be displayed using box-plot.

Subject data listings of Laboratory test results and TEMA will be provided.

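### ECG, chest x-ray and neurological summaries have no discontinuation or worst-value row, the Table 8.4 Week 52 window misses the scheduled visit, and the ECG and x-ray categories omit clinically significant abnormality

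*SAP*

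**What the plan says.** **What is collected.** Protocol Table 4 marks ECG, chest x-ray and neurological findings in the discontinuation column. Protocol 9.5.5 makes that visit a general requirement: "All subjects who discontinue the study are to complete" the early discontinuation procedures. For ECG, Protocol 9.5.1.5.6 says the investigator "records the results (abnormal or normal) in the CRF". Section 9.5.1.5.7 sets the same two-level entry for chest x-ray.

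**What is tabulated.** SAP 5.6.5 (ECG) and 5.6.6.1 (chest x-ray) plan shift tables by visit and treatment group, with the levels "normal/abnormal, not clinically significant/abnormal, not clinically significant". SAP 5.6.6.2 says: "Descriptive statistics for neurological findings will be presented by visit and treatment group". Listings are planned for all three assessments.

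**How a visit is defined.** SAP 8.1.3 assigns results to visits by time window. Table 8.4 is headed "Definition of time windows and calculated visits for 12-lead ECG, Chest x-ray, Pregnancy test, Blood CD4 positive cells" and Table 8.6 "Definition of time windows and calculated visits for Neurological findings, Vasculitis marker tests". Every row in both has the window "Base date - 14 days <= < Base date + 14 days". Neither has a row for discontinuation or end of treatment.

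**What the SAP does elsewhere.** For laboratory values, SAP 5.6.3 plans shift tables that "compare the baseline LNH classification to the LNH classification at each postbaseline visit and at the end of treatment", and similar tables for the highest and lowest value during the study.

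**The concern.** A subject who stops between windows has an ECG, a chest x-ray and a neurological examination that the protocol requires, but the three SAP sections give those results no row in a summary table. The last-observation rule for safety data in SAP 5.3.5 does not fill the gap, because it is limited to continuous values and these three are categorical.

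By-visit tables built this way mainly describe subjects who stayed on treatment. Safety and tolerability is a primary objective, and the protocol synopsis promises the frequency and percentage of abnormal findings by treatment group for these assessments. A summary that leaves out most discontinuation visits could understate that frequency. The documents do not let one say by how much.

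The category list is a separate fault with a related effect. As printed, a clinically significant ECG or x-ray abnormality has no cell, and the protocol gives no sign that the CRF separates clinically significant from other abnormalities.

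**Working it through.** **Base dates (SAP Table 8.4): week × 7 against the printed offset**

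| Visit | Week × 7 | SAP offset (days after first dose) | Agrees |
|---|---|---|---|
| Week 24 | 168 | 168 (from the X × 7 rule) | yes |
| Week 52 | 364 | 334 | no |
| Week 76 | 532 | 532 | yes |
| Week 104 | 728 | 728 | yes |

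The printed Week 52 window runs from 334 − 14 = 320 to 334 + 13 = 347, since the upper end is excluded. Protocol 9.5.2.1 allows ±7 days after Week 14, so the on-schedule Week 52 visit falls on days 357 to 371. None of those days is in the window. Table 8.6 uses X × 7 for Week 52, so neurological findings are unaffected.

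**Coverage of the extension period.** Days 168 to 727 are 560 days. Coverage = days inside any window / 560.

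- Table 8.4 as printed (ECG, chest x-ray): days 168–181 (14), 320–347 (28), 518–545 (28) and 714–727 (14). Sum 84; 84/560 = 15%, leaving 85% outside.
- Table 8.4 with Week 52 at 364: the 28-day window moves to 350–377. The total stays 84/560 = 15%.
- Table 8.6 (neurological): Week 24 gives 14 days; Weeks 36, 52, 64, 76 and 88 give 5 × 28 = 140; Week 104 gives 14. Sum 168; 168/560 = 30%, leaving 70% outside.

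Example: a chest x-ray and neurological examination at a Week 60 discontinuation (60 × 7 = day 420) fall in no window of either table.

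**Sensitivity to timing.** The documents give neither the number nor the timing of discontinuations, so an even spread is an assumption. Share covered under other patterns:

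| Discontinuation pattern | ECG, chest x-ray (Table 8.4 as printed) | Neurological (Table 8.6) |
|---|---|---|
| Even over days 168–727 | 15.0% | 30.0% |
| Constant hazard, 20% to 60% total dropout | 15.1% to 15.3% | 30.1% to 30.2% |
| Front-loaded, 12-week half-life | 18.2% | 31.5% |
| Only in Weeks 76–104 | 14.3% | 28.6% |
| Even over the 39 two-weekly visits, Weeks 26–102 | 5/39 = 12.8% | 11/39 = 28.2% |

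Most results are outside the windows in every pattern tried. That would reverse only if more than half of the discontinuations clustered in the 15% or 30% of days that are covered.

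**Categories.** The SAP prints three levels, of which the second and third are identical. The protocol has two levels at data entry (9.5.1.5.6, 9.5.1.5.7) and in its planned shift tables (9.7.1.8.5, 9.7.1.8.6). The SAP list matches neither the protocol nor a complete three-level scheme.

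**The case against.** **The results are not lost from the report.** A reader might infer that discontinuation results disappear. They do not: all three sections plan subject listings. The loss is from summary tables. This stands.

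**The PML screen does not depend on these tables.** A reader might also infer that a PML signal at discontinuation would go unseen. Protocol 9.5.1.5.7 requires neurological abnormalities appearing after dosing to be reported to the sponsor at once, evaluated and recorded as adverse events, at scheduled or unscheduled times. SAP 5.6.2 tabulates TEAEs up to 70 days after the last dose, without visit windows. A new neurological abnormality therefore reaches a summary table. This stands, and it moves the weight of the point to ECG and chest x-ray, where an abnormality becomes an adverse event only if it meets the definition.

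**CD4 is in Table 8.4 but is not affected in the same way.** It is continuous, and SAP 5.3.5 applies a last-observation rule by phase to continuous safety values. This stands for its descriptive statistics.

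**The windows may not be exhaustive.** Laboratory Table 8.3 has no end-of-treatment row either, yet SAP 5.6.3 tabulates end of treatment. The programming specifications and table shells are separate documents (SAP 9 and 11). So the SAP's silence does not prove that discontinuation results will be excluded. But 5.6.3 names the extra comparison in its text and these three sections do not. Followed as written, they tabulate by visit only.

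**The percentages are shares of days, not of subjects.** Reading 85% and 70% as known fractions of discontinuation results goes further than the documents allow. Nor do they show that subjects stop mainly because of a safety problem: Protocol 9.5.5 also lists subject choice, inadequate effect and withdrawal of consent.

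**The protocol does not promise last-value or worst-value rows, and no extension inference is at stake.** Both are true. The case rests on completeness of safety reporting and on the SAP's own laboratory practice.

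**Conclusion.** The point holds in a limited form.

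- As written, the by-visit summaries have no place for most discontinuation-visit ECG, chest x-ray and neurological results. Window coverage is 15% of extension days for ECG and chest x-ray and 30% for neurological findings. The word most assumes that discontinuations are not concentrated in the windows; the patterns tried give 13% to 18% and 28% to 32%.
- The material loss is ECG and chest x-ray abnormalities that were not judged to be adverse events. Listings hold all results, and the TEAE tables hold the rest of the important ones, including new neurological abnormalities. The number of subjects affected cannot be derived from the documents.
- The Week 52 base date in Table 8.4 is an arithmetic error that depends on no assumption: on-schedule Week 52 ECGs and chest x-rays fall outside every window.
- The repeated category is most likely a slip of wording. As printed it still leaves clinically significant abnormalities without a cell, and it does not match the normal/abnormal data that the protocol says are collected.

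**What to change.** 1. In SAP 5.6.5, 5.6.6.1 and 5.6.6.2, add one row for the last on-treatment or discontinuation result and one for the worst post-baseline result, following the end-of-treatment and extreme-value approach of 5.6.3. Every discontinuation result then enters a summary table.
2. In Table 8.4, change the Week 52 base date to +364 days. The same +334 appears in Tables 8.5, 8.7 and 8.9 to 8.12 and should be corrected there too. This step alone leaves ECG and x-ray coverage at 15%, so it does not replace step 1.
3. For ECG and chest x-ray, use normal/abnormal as collected. If the CRF does hold clinical significance, make the third level abnormal and clinically significant.

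The cost is a few extra table rows and two text corrections. No new data are needed.

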The last subject entered the Extension Phase (open-label) in March 2018, and all subjects had completed 52 weeks of treatment with E6011 by March 2019. Consequently, it was

considered unnecessary to conduct any non-safety assessments after March 2019, and the protocol will be revised to Version 6.

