9.5.2 Schedule of Procedures/Assessments

9.5.2.1 Study Schedule

[Table 4](#) presents the schedule of procedures/assessments for this study.

Each assessment will be performed within 3 days before or after the scheduled date during Weeks 1 to 12 or within 7 days before or after the scheduled date after Week 14 using Week 0 as a reference point. In the Follow-up Phase, each assessment will be performed within 7 days before or after the scheduled date (“within 7 days after the scheduled date” for

the assessments at “70 days after the last dosing”). However, the interval between study treatments should be at least 3 days until 2 weeks after the start of study treatment, and at least 6 days after 4 weeks have elapsed since the start of study treatment. If any scheduled assessment or administration of the study drug cannot perform within the above period, each assessment will still be performed, but administration of the study drug will be skipped.

After the date Version 6 of the protocol is approved by IRB, it is unnecessary to conduct "tender and swollen joint counts/ESR", "VAS/HAQ", "RF/anti-CCP antibody/MMP-3", "serum E6011 concentration", "serum anti-E6011 antibody", "serum total FKN concentration", "cytokines/LRG1/Ang2", "TRACP-5b", "CX3CR1-positive cell count", or "VectraTM DA". However, assessments of "serum E6011 concentration" and "serum anti-E6011 antibody" will be conducted at discontinuation.

Table 4 Schedule of Procedures/Assessments in Study E6011-J081-201

Phase	Screen-ing	Obser-vation	Treatment							
			W0		W1	W2	W4	W6	W8	W10
Assessment	Time postdose Day -42 to Day -1	Day 1		Day 8 ±3 days	Day 15 ±3 days	Day 29 ±3 days	Day 43 ±3 days	Day 57 ±3 days	Day 71 ±3 days	Day 85 ±3 days
		Pre	Dosing							
Informed consent	X									
Demographics, medical history, complication	X									
Inclusion/exclusion criteria	X	X								
Study drug administration ^a			X	X	X	X	X	X	X	X
Prior treatment / concomitant medication or therapy										
Vital signs	X	X		X	X	X		X		X
Height / body weight ^b	X ^b									X
Physical findings, injection site finding ^c	X	X		X	X	X		X		X
Standard 12-lead ECG		X								X
Chest x-ray	X									X
Pregnancy test ^d	X	X ^d								X
Neurological findings ^e	X									X
Anti-JCV antibody test	X									
Blood CD4-positive cells	X									X
Viral test, syphilis test, TB test	X									
Number of tender / swollen joints, ESR	X	X			X	X		X		X
VAS, HAQ		X			X	X		X		X
Joint x-ray	X									

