- a. Study drug will be administered upon completion of all the planned investigations (except for injection site findings) on the day.
- b. To measure height only at the Screening Phase and W52.
- c. To examine injection site findings after study drug administration.
- d. To perform pregnancy test in women of childbearing potential. On-site test conducted at the Observation Phase only.
- e. If any postdose abnormality is observed in neurological examination, head MRI (T1-weighted image, FLAIR image, diffusion-weighted image) will be performed within 2 weeks along with consultation to a neurologist.
- f. The interval between study treatments is at least 7 days (at least 6 days between treatments)
- g. Administration of study drug at Week 24 is done in an open-label manner.
- h. W52+2n: W54, 58, 62, 66, 70, 74, 78, 82, 86, 90, 94, 98, 102
- i. W52+4n: W56, 60, 68, 72, 80, 84, 92, 96
- j. Basically performed at study discontinuation, and a missing value is permissible only when collection of the sample is difficult due to abrupt discontinuation.
- k. Will only be conducted if blood sample is judged to be feasible at the visit.
- l. After the date Version 6 of the protocol is approved by IRB, applicable assessments will not be conducted. However, assessments of serum E6011 concentration and serum anti-E6011 antibody will be conducted at discontinuation.

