9.5.2.2 Volume of Blood Samples

Table 5 shows the frequency of blood samplings and volume of blood samples obtained throughout the study period. If any deviation from reference range or any finding for which the investigator or subinvestigator considers it necessary to confirm the subject's safety, the required volume of blood samples may increase from the specified volumes tabulated below.

As it is unnecessary to conduct non-safety assessments after the date Version 6 of the protocol is approved by IRB, the volume of blood samples may be lower in applicable subjects.

Table 5 Volume of Blood Samples

Test item	Volume per sampling	Screening Phase	Observation Phase	Treatment Phase	Extension Phase	Follow-up Phase
		Days -42 to -1	Predose of Day 1	Weeks 1 to 24	Weeks 26 to 104	
Viral test, syphilis test, TB test	26 mL	once			twice	
Erythrocyte sedimentation rate	2 mL	once	once	7 times	20 times	
Hematology	2 mL	once	once	7 times	20 times	once
Blood chemistry		once	once	7 times	20 times	once
Pregnancy test	10 mL	(once) ^a		(twice) ^a	(3 times) ^a	
Serum KL-6		(once) ^a		(twice) ^a	(twice) ^a	
Anti-JCV antibody test	3 mL	once		once	3 times	
Blood CD4-positive cells	2 mL	once		twice	3 times	
RF, anti-CCP antibody, MMP-3	4 mL	once	once	7 times	20 times	once
Autoantibody	3 mL		once	twice	3 times	
Serum TRACP-5b concentration			(once) ^a	(twice) ^a	(twice) ^a	
β-D glucan	3 mL	once		twice	twice	
Vasculitis marker tests	5.8 mL		once	twice	6 times	
Serum E6011 concentration	2 or 5 mL		once ^b	8 times ^b	20 times ^b	
Serum anti-E6011 antibody			once ^b	6 times ^b	20 times ^b	
Serum total FKN			(once) ^a			
Serum cytokine concentration, serum LRG1, and Ang2	5 mL		once	3 times	twice	
Vectra TM DA			(once) ^a	(twice) ^a	(twice) ^a	
Immunocytes such as blood CX3CR1-positive cells	5 mL		once	4 times	once ^c	Once ^d
Total volume of blood samples						
Each Phase		52.0 mL	41.8 mL	225.6 mL	591.8 mL	16 mL
Screening to Week 24			319.4 mL			
Screening to Week 104				911.2 mL		
Screening to the Follow-up Phase					932.2 mL	

a: Blood collections for these items (inside the brackets) are included in those for the items just above.

b: The volume of blood sample is 5 mL at the time point for assessing both serum E6011 concentration and serum anti-E6011 antibody and 2 mL at the time point for assessing serum E6011 concentration only.

c: Twice for subjects who discontinue treatment later than Week 52

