5.5.2.2 Other Biomarker Analyses

All biomarker analyses will be performed using the Full Analysis Set.

For the Extension Phase, summary statistics for serum RF concentration, serum anti-CCP antibody concentration, and serum matrix metalloproteinase-3 concentration, serum tartrate resistant acid phosphatase 5b (TRACP-5b) concentration, serum cytokine concentration, serum leucine-rich alpha-2 glycoprotein 1 (LRG1) concentration, serum angiopoietin 2 (Ang2) concentration, Vectra™ DA and its component (vascular cell adhesion molecule-1 (VCAM-1), epidermal growth factor (EGF), vascular endothelial growth factor (VEGF)-A, interleukin (IL)-6, tumor necrosis factor receptor-I (TNF-RI), serum matrix metalloproteinase-1, serum matrix metalloproteinase-3, YKL-40, leptin, resistin, SA and CRP) value, change from baseline and percent change from baseline, by treatment group and time point, will be calculated. Exploratory investigations of the relationship between efficacy and biomarkers will be conducted. The analysis plan for CX3CR1 is out of scope of this document. All other biomarkers will be collected on baseline and postbaseline, referring [section 8.1.3](#) "Time window".

Subject data listings will be provided.

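### Seven SAP time-window tables place Week 52 at day 334 instead of day 364, so on-schedule Week 52 results for nine ECG, imaging, cell-count and biomarker items fall in no analysis window

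*SAP*

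**What the plan says.** The Week 52 rows of SAP Tables 8.4, 8.5, 8.7, 8.9, 8.10, 8.11 and 8.12 all give the base date as "Date of first drug administration + 334 days". The window is 14 days either side (upper end exclusive) in every one of these tables except 8.12 (joint x-ray), where it is 28 days.

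Tables 8.1, 8.2, 8.3, 8.6 and 8.8 instead cover Week 52 by a formula, "Date-time of first drug administration + X * 7 days (Week X", which gives 364 days.

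Protocol section 9.5.2.1 has later visits assessed "within 7 days before or after the scheduled date after Week 14 using Week 0 as a reference point".

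Several planned outputs are by visit or time point:
- Biomarkers (SAP 5.5.2.2): "change from baseline and percent change from baseline, by treatment group and time point, will be calculated". The same section says "All other biomarkers will be collected on baseline and postbaseline, referring" section 8.1.3.
- ECG, chest x-ray and CD4 (SAP 5.6.5, 5.6.6.1, 5.6.6.3): by-visit shift tables or summaries.
- Laboratory parameters (SAP 5.6.3): summaries at each postbaseline visit.

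The selection rule in section 8.1.3 only chooses among several observations inside one window. It does not assign an observation that lies outside every window.

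**The concern.** The Week 52 anchor is 30 days too early (364 − 334). In the ±14-day tables the window therefore closes before the visit may take place. A Week 52 row could then hold only off-schedule data, such as a discontinuation visit on days 320 to 347, shown under a Week 52 label.

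The loss matters most where there are few time points. In Protocol Table 5 the row for "Serum cytokine concentration, serum LRG1, and Ang2" shows two Extension Phase samples. TRACP-5b and Vectra DA have the same two, at Weeks 52 and 104. Version 6 then stopped these samples (Protocol Table 4, footnote l): "After the date Version 6 of the protocol is approved by IRB, applicable assessments will not be conducted". Protocol section 7 states that "The last subject entered the Extension Phase (open-label) in March 2018", so some subjects could not have reached Week 104 before the stop. For those still on study at that point, Week 52 is the only scheduled Extension Phase biomarker value.

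On the safety side, Week 24 assessments come before that day's dose (Table 4, footnote a). For subjects randomized to placebo, Week 52 is thus the first scheduled ECG, chest x-ray and CD4 count after exposure to E6011.

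**Working it through.** Days are counted from first dose (first dose = day 0).

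**1. The anchors, by the SAP's rule of weeks × 7**
- Week 24: 24 × 7 = 168, as stated.
- Week 76: 76 × 7 = 532, as stated.
- Week 104: 104 × 7 = 728, as stated in these tables.
- Week 52: 52 × 7 = 364; stated 334. The stated figure cannot be reproduced: 334 / 7 = 47.7 weeks, and shifting by one day gives only 363 or 365.

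**2. Permitted Week 52 days**

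364 ± 7 = days 357 to 371, which is 15 days.

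**3. Windows as written and as corrected**

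| SAP table | Items | Week 52 window as written | Permitted days caught by any row | With 364 |
|---|---|---|---|---|
| 8.4 | ECG, chest x-ray, pregnancy test, CD4 | 320–347 | 0 of 15 | 350–377: 15 of 15 |
| 8.5 | body weight, autoantibody | 320–347 | 0 of 15 | 15 of 15 |
| 8.7 | KL-6, β-D glucan, TRACP-5b, Vectra DA | 320–347 | 0 of 15 | 15 of 15 |
| 8.9 | cytokines, LRG1, Ang2 | 320–347 | 0 of 15 | 15 of 15 |
| 8.10 | anti-JCV antibody | 320–347 | 0 of 15 | 15 of 15 |
| 8.11 | virus, syphilis, TB | 320–347 | 0 of 15 | 15 of 15 |
| 8.12 | joint x-ray | 306–361 | 5 of 15 (357–361) | 336–391: 15 of 15 |

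In the ±14-day tables the last day of the window (347) is 10 days before the first permitted day (357). The neighbouring rows do not help: Week 24 ends at day 181, Week 36 at day 265, Week 76 starts at day 518 and Week 104 at day 714. In Table 8.12 the Week 76 row starts at day 504.

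**4. Items with a second, correct table**

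SAP 5.6.4 lists weight among the vital signs (Table 8.1). Protocol Table 3 lists KL-6 and β-D glucan under blood chemistry (SAP Table 8.3). Both tables give a window of 350–377 and catch 15 of 15 days. For these three items the tables conflict, so the result is not simply lost.

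**5. Scheduled Extension Phase time points lost**
- ECG, chest x-ray, CD4: 1 of 3 (Weeks 52, 76, 104).
- Autoantibody: 1 of 3 (Weeks 36, 52, 104).
- TRACP-5b, Vectra DA, cytokines, LRG1, Ang2: 1 of 2 (Weeks 52, 104).

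**6. Who has only Week 52 for the biomarkers**

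From Extension entry (Week 24) to Week 104 is 80 weeks, or 560 days. Version 6 is dated 25 March 2019, and 560 days before that is 11 September 2017. Subjects who entered after about that date and were still on study had not reached Week 104. The cut-off moves later if a site's IRB approved later.

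**7. mTSS**

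The formula in SAP 5.3.5 has unbalanced brackets. Read as linear extrapolation, the change at Week 52 is the observed change × 52 / (study day / 7), with study day = days after first dose + 1.
- Film on day 362: 364 / 363 = 1.003.
- Film on day 364: 364 / 365 = 0.997.
- Film on day 371: 364 / 372 = 0.978.

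If a film outside the window were instead treated as missed, the Week 24 film would be carried forward.
- Film on day 168: 364 / 169 = 2.154 times its change.
- Range for films on days 161 to 175: 364 / 162 = 2.247 to 364 / 176 = 2.068.

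On that second reading, subjects whose treatment changed at Week 24 would have no value. The change is clear for placebo and 100 mg, at most 50 + 25 = 75 of 175 planned subjects (43%). It does not apply to the 200 mg arm, unless going open-label or a later dose increase counts as a change. It is uncertain for the 400 mg arm, which is on 200 mg from Week 12.

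**The case against.** The strongest reply is that this is one copied constant whose intent is plain. The rows are labelled Week 52, they sit beside tables that give 364, and an empty Week 52 column would probably be noticed in programming. All affected outputs are descriptive and open-label, and the listings keep every value. This limits the harm but does not make the written rule right. SAP section 9 puts the programming rules in separate documents, so the reader cannot tell which figure was used.

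Narrower points:
- **Reach of section 8.1.3.** Its opening sentence refers only to Tables 8.1 to 8.8. Read literally, cytokines, LRG1, Ang2 and joint x-ray are outside it. Tables 8.4, 8.5 and 8.7 are inside, so ECG, chest x-ray, CD4, autoantibody, TRACP-5b and Vectra DA are affected either way.
- **By visit could mean the nominal visit.** The ECG, chest x-ray and CD4 sections do not say which is meant. The table headings speak of calculated visits, and the biomarker section points to 8.1.3, so the calculated visit is the better reading.
- **Autoantibody.** Table 8.3 covers laboratory tests, and Protocol Table 3 lists autoantibody as one. But Table 8.3 names blood chemistry and not autoantibody, which has its own row in Table 8.5. The point is arguable but does not change the result.
- **The calendar cut-off.** SAP section 3 calls Week 84 the latest visit of ongoing subjects at the amendment. Taken literally, they entered the Extension Phase no earlier than about 29 January 2018 (60 weeks before 25 March 2019). The group with only Week 52 would then be smaller. Subjects who discontinued before Version 6 also had a discontinuation sample. This objection stands: the size of the group is unknown.
- **mTSS.** The factor near 2.15 and the 43% depend on a reading the text does not favour, and 43% is an upper bound. They should carry little weight.

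**Conclusion.** The concern holds. Followed as written, Tables 8.4, 8.5, 8.7 and 8.9 place none of the 15 permitted Week 52 days in any window. The planned Week 52 summaries for ECG, chest x-ray, CD4, autoantibody, TRACP-5b, Vectra DA, cytokines, LRG1 and Ang2 would be empty or filled with off-schedule data. This assumes that by-visit outputs use the calculated windows and that 334 was programmed; the second cannot be checked from the documents.

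For weight, KL-6 and β-D glucan the SAP contradicts itself. For joint x-ray, 10 of 15 permitted days, including day 364 itself, are outside the Week 52 window. The effect on mTSS is probably small (factor 0.98 to 1.00), because the extrapolation uses the film's actual day and a film taken on day 364 was not missed. Tables 8.10 and 8.11 feed no planned by-visit summary.

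Not affected are:
- the Week 12 primary analysis;
- listings, highest/lowest and end-of-treatment laboratory shifts, last-observation-of-phase summaries and TEMAVs;
- ACR components, DAS28, SDAI and CDAI;
- routine laboratory tests, RF, anti-CCP, MMP-3, anti-E6011 antibody, vasculitis markers and neurological findings.

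It should be fixed, but it does not threaten the trial's main conclusion.

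**What to change.** Replace 334 with 364 in the Week 52 rows of Tables 8.4, 8.5, 8.7, 8.9, 8.10, 8.11 and 8.12, and search the programs for the same constant. All 15 permitted days then fall in the Week 52 window in all seven tables.

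For consistency, change the Week 104 base date in Table 8.2 from 168 to 728 days; no planned summary uses that row.

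The cost is one constant in seven rows, one consistency edit and a check of the programmed visit windows. No new data or analyses are needed.
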